12.4 Secondary Analysis

Secondary endpoints: Response rate, overall survival, and duration of response (please see section 10.1).

12.4.1 Analysis Population

All Treated Subjects: All subjects who received at least one dose of pembrolizumab and completed the prescribed course of palliative radiation therapy.

12.4.2 Analysis Plan

Data will be summarized using appropriate descriptive statistics: proportions with Wilson's 95% confidence intervals, means, standard deviations, ranges, and Kaplan-Meier estimates for time to event data. The toxicity rates will be monitored continuously and a final count of toxicities will be performed.

12.5 Sample Size

A sample of 30 patients would provide 87% power to ensure a half-width of 15.5% of the 95% confidence interval using Wilson's method assuming that the observed rate is 20%. If the observed rate is exactly 20% then the 95%CI using Wilson's method will be [9.5%, 37.3%].

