1. OBJECTIVES

1.1. Primary Objective

The primary objectives of this study are to assess 1) the safety and 2) efficacy of combining Anti-PD-1/PD-L1 blockade with palliative radiation therapy in patients with Stage IV Merkel Cell Carcinoma. Efficacy for the primary objective will be tumor response rates (CR, PR, SD, irCR, irPR, irSD) at both irradiated and unirradiated sites.

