Pembrolizumab (Keytruda) is a PD-1 blocking antibody, approved for multiple indications, and most recently in December 2018, approved for recurrent locally advanced or metastatic MCC. The approval was based on the Phase II CITN-09/KEYNOTE-017 trial in which pembrolizumab resulted in an Overall Response Rate (ORR) of 56%, PR rate of 32% and CR rate of 24% in patients who had not previously received systemic therapy for their advanced disease. An additional 10% had stable disease. In this multicenter, single arm trial, 50 treatment naïve patients were treated with pembrolizumab at 2 mg/kg every 3 weeks. 86% of patients had metastatic disease and 64% were positive for Merkel cell polyomavirus (MCPyV). At a median follow up of 14.9 months the median duration of response (DOR) was not reached. Among the 28 patients with response, 96% had a DOR of at least 6 months, and 54% had a DOR of 12 months or more. Both Progression Free Survival (PFS) and median Overall Survival (OS) with pembrolizumab were higher than historical data for chemotherapy controls. The median time to response was 2.8 months, with most responses occurring by 12 weeks. Responses were observed regardless of Merkel cell polyomavirus (MCPyV) status, with an ORR of 59% in MCPyV-positive patients and 53% among MCPyV-negative patients. The most common AEs of pembrolizumab reported in at least 20% of patients who received single-agent pembrolizumab were fatigue, musculoskeletal pain, decreased appetite, pruritus, diarrhea, nausea, rash, pyrexia, cough, dyspnea, constipation, pain and abdominal pain. Overall, 96% of patients experienced all-grade treatment-related AEs, with 14% of patients discontinuing treatment due to treatment-related AEs. Grade 3 and above treatment-related AEs were reported for 28%, and there was one treatment-related death in this study.

Additional information regarding pembrolizumab (e.g. PK, route of elimination, metabolism, etc.) can be found in the package insert.

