12.2 Interim Analyses

An interim analysis for futility will be performed after 15 patients have completed the treatment phase. A response rate of 20% is expected, so if one or fewer of 15 patients have demonstrated a PR or CR, the study will be stopped for futility.

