12.3 Primary Analysis

Primary Endpoint: The determination of the complete response rate and the 95%CI using Wilson’s method

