12.3.1 Analysis Population

All Treated Subjects: All subjects who received at least one dose of pembrolizumab and completed the prescribed course of palliative radiation therapy.

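### Section 12.5 conditions its 87% on an observed rate of 20% when it holds for a true rate, and names no endpoint; response is not split by prior anti-PD-1/PD-L1 treatment

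*Combined protocol and SAP*

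**What the plan says.** Section 12.5 (Sample Size) states: "A sample of 30 patients would provide 87% power to ensure a half-width of 15.5% of the 95% confidence interval". It continues "assuming that the observed rate is 20%. If the observed rate is exactly 20% then the 95%CI" and gives that interval as 9.5% to 37.3%. It does not say which rate is meant.

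Other sections point to different rates:

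- Section 1.1: "Efficacy for the primary objective will be tumor response rates (CR, PR, SD, irCR, irPR, irSD) at both irradiated and unirradiated sites".
- Section 12.2: "A response rate of 20% is expected, so if one or fewer of 15 patients have demonstrated a PR or CR".
- Section 12.3, primary endpoint: "The determination of the complete response rate and the 95%CI using" Wilson's method.
- Section 12.4: "Secondary endpoints: Response rate, overall survival, and duration of response".

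The synopsis gives the sample size as 30 participants. Section 12.3.1 restricts the analysis to "All subjects who received at least one dose of pembrolizumab and completed the prescribed course of palliative radiation therapy", and Section 12.4.1 uses the same set.

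Section 2.4 takes patients as first-line treatment or after progression on earlier therapy, and Section 4.1.1 admits patients with prior anti-PD-1/PD-L1 treatment case by case. Sections 12.3 and 12.4 plan pooled summaries only. The pembrolizumab benchmark in Section 2.2 is an "Overall Response Rate (ORR) of 56%, PR rate of 32% and CR rate of 24% in patients who had not previously received systemic therapy".

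**The concern.** An interval width is fixed once the result is observed, so it cannot have an 87% chance of being reached at an observed rate. A probability needs a true rate as its condition. The sentence that justifies the sample size is therefore wrong as worded.

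The missing endpoint matters more. The planned precision could be nearly assured or unlikely, depending on whether the 20% is complete response, PR+CR, or CR+PR+SD. The plan points to each of these somewhere.

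The pooled response rate is a separate matter. The protocol's pembrolizumab benchmark comes from patients without earlier systemic therapy for advanced disease. A rate that mixes in patients already exposed to the same drug class cannot be set directly against it.

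**Working it through.** **Inputs.** n = 30, target half-width 15.5 points, rate 20% and a 95% Wilson interval come from Section 12.5. The futility rule (stop if 0 or 1 of 15 respond) is in Section 12.2. Section 2.2 gives avelumab 33% overall and 11.4% complete response, and pembrolizumab 56% overall, 24% complete response and a further 10% stable disease (56 + 10 = 66%).

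**Formula.** With z = 1.96 and p̂ = x/n, half-width = z/(1 + z²/n) × √[p̂(1 − p̂)/n + z²/(4n²)]. At n = 30 the multiplier is 1.7375 and z²/(4n²) = 0.001067.

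**Observed 20%, as written.** For x = 6: 1.7375 × √(0.16/30 + 0.001067) = 0.139. The centre is (0.2 + 3.8415/60)/1.128 = 0.234, so the interval is 9.5% to 37.3%, as the plan states. The half-width is 13.9 points and the target is met with certainty.

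**True 20%.** The half-width is 15.13 points at x = 8, 15.61 at x = 9, and at most 16.85 at x = 15. It is symmetric, so the target is met for x = 0–8 and 22–30. Summing Binomial(30, 0.20) over these counts gives 0.8713, which is the plan's 87%.

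**Same sum at the Section 2.2 rates, n = 30.**

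| Endpoint | True rate | P(half-width ≤ 15.5) |
|---|---|---|
| Complete response | 11.4% (avelumab) | 99.5% |
| Complete response | 24% (pembrolizumab) | 71.9% |
| PR+CR | 33% (avelumab) | 29.9% |
| PR+CR | 56% (pembrolizumab) | 4.1% |
| CR+PR+SD | 66% (pembrolizumab) | 26% |

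**Futility rule, if the 20% is PR+CR.** P(0 or 1 of 15) = 0.8¹⁵ + 15 × 0.2 × 0.8¹⁴ = 0.0352 + 0.1319 = 0.167. The chance of both passing the interim (at least 2 of 15) and ending with a total that meets the target is 0.705. Given continuation it is 0.705/0.833 = 0.846. The 70.5% counts a stopped trial as not delivering the 30-patient interval.

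**Fewer than 30 analysed (assumed losses of 1 to 3).** The maximum half-width is 17.1 points at 29, 17.4 at 28 and 17.6 at 27.

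**Descriptive subgroups (assumed sizes).** At an observed 20% the half-width is 16.8 points for 4/20, 19.1 for 3/15 and 22.7 for 2/10.

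**The case against.** The strongest reply is that this is a slip of wording. Both figures in Section 12.5 reproduce, the intended meaning is recoverable, the analysis is descriptive with no test to lose power, and the target is missed by at most 16.85 − 15.5 = 1.35 points. All of that stands, and it limits the weight of the point. It does not supply the missing endpoint.

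A reader might infer more than the documents support:

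- *The 87% holds only at exactly 20%.* It does not. The chance is higher at lower rates (97.2% at 15%) and lower at rates moderately above 20%.
- *Losing one patient cuts the assurance to 79.0%.* That figure arises because 8/29 has a half-width of 15.509 points, 0.009 over the cut-off. Counting it as 15.5 gives 89.2%. With 28 analysed the chance is 81.8%, above the 79.0% at 29. The probability jumps with discreteness, so the maximum half-width is the more useful summary.
- *The plan leaves open what 30 counts.* The synopsis says 30 participants, which reads as enrolment. What is missing is any allowance for patients who fall outside Section 12.3.1.
- *The pooled rate is invalid, or its case-mix bias can be calculated.* The pooled rate validly describes the patients enrolled. The documents give no response rate for patients previously exposed to anti-PD-1/PD-L1 (the avelumab figures are from use after chemotherapy) and no expected share of such patients. No numerical illustration is justified.

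It can also be said that the Section 2.2 rates are not design assumptions. That is true; they serve here only to show how far the precision statement depends on the endpoint.

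**Conclusion.** The point holds as a correction to the justification of the sample size, not as a case for more patients. The 87% is numerically right for a true rate of 20% with all 30 patients analysed, and wrong as conditioned on an observed 20%. Without a named endpoint a reader cannot tell whether the planned precision is nearly certain (99.5%) or unlikely (4.1%) at the protocol's own cited rates. The practical effect is bounded: the half-width cannot exceed 16.9 points at 30 analysed, or 17.6 at 27.

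If the endpoint is PR+CR, the futility rule also matters: 84.6% given continuation and 70.5% overall at a true 20%. For another endpoint the effect of that rule depends on the PR+CR rate as well and cannot be derived from the 20% alone.

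The missing split by prior anti-PD-1/PD-L1 treatment is a separate gap in reporting. It rests on who may enrol and where the benchmark comes from, not on any estimate of bias. These calculations assume independent patients with a common true rate.

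**What to change.** **Section 12.5.** After the sponsor has reconciled Section 1.1 with Section 12.3, name the endpoint and write: *If the true rate is 20% and 30 patients are analysed, the probability that the 95% Wilson half-width is at most 15.5% is 87%; at n = 30 the half-width never exceeds 16.9%.* Then:

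- add the probability at the Section 2.2 rates for that endpoint only, from the table above;
- if the endpoint is PR+CR, add that at a true 20% the Section 12.2 rule stops 16.7% of trials at 15 patients, so the probability is 84.6% given continuation and 70.5% overall;
- say that the figure assumes all 30 participants enter the Section 12.3.1 population, and give the maximum half-width for 27 to 29 analysed (17.6 to 17.1 points) rather than a probability at each n.

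**Sections 12.3 and 12.4.** Add: *The complete response rate and the response rate will also be reported, with descriptive 95% Wilson intervals, separately for patients with and without prior anti-PD-1/PD-L1 treatment.*

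**Cost.** Some rewording, one added sentence in each of Sections 12.3 and 12.4, and one sponsor decision on the endpoint; no added patients. The precision statement will look less favourable if the endpoint is PR+CR or CR+PR+SD. The subgroup intervals will be wide, about 17 to 23 points half-width at an observed 20% with 20 down to 10 patients, and can only be descriptive.

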APPENDIX 1: ECOG PERFORMANCE STATUS

ECOG PERFORMANCE STATUS*	
Grade	ECOG
0	Fully active, able to carry on all pre-disease performance without restriction
1	Restricted in physically strenuous activity but ambulatory and able to carry out work of a light or sedentary nature, e.g., light house work, office work
2	Ambulatory and capable of all self-care but unable to carry out any work activities. Up and about more than 50% of waking hours
3	Capable of only limited self-care, confined to bed or chair more than 50% of waking hours
4	Completely disabled. Cannot carry on any self-care. Totally confined to bed or chair
5	Dead

APPENDIX 2: PARTICIPANT ELIGIBILITY CHECKLIST

A Participant Eligibility Checklist must be completed in its entirety for each subject prior to registration. The completed, signed, and dated checklist must be retained in the patient's study file.

The study coordinator, treating physician and an independent reviewer must verify that the participant's eligibility is accurate, complete, and legible in source records. A description of the eligibility verification process should be included in the EPIC or other Electronic Medical Record progress note. **I. Protocol Information:**

Protocol Title:	A Phase II Study of Palliative Radiation Therapy and Anti-PD-1/PD-L1 Checkpoint Blockade in Patients with Metastatic Merkel Cell Carcinoma, Amendment 2, September 10, 2019
Protocol Number:	OnCore: SKIN0047 IRB: 50888
Principal Investigator:	[name], MD

II. Subject Information:

Subject ID/Initial:	
Gender:	 Male  Female

III. Study Information:

SRC Approved IRB Approved

IV. Inclusion/Exclusion Criteria

	Patient Selection	Window	Last Date to Register	Supporting Documentation	Location of Document	Yes	No
	Signed and Dated Informed Consent Form	NA		Signed ICF date:			
3. 1. 1	Histologically confirmed metastatic or locally advanced Merkel Cell Carcinoma (includes in-transit or bilateral bulky disease) with at least two distinct sites of disease.	NA		Bx Date:			
3. 1. 2	Subjects with brain metastases and/or carcinomatous meningitis are eligible providing they are neurologically	NA					

	stable (if systemic steroids are required, subjects should be stable on the lowest clinically effective dose, as steroids may interfere with the activity of immunotherapy if administered at the time of the first Anti-PD-1/PD-L1 dose.)						
3.1.3	Must be at least 14 days since treatment for MCC, and recovered (baseline or residual non ir Grade 1 toxicity or ir Grade 2 toxicity at the investigator's discretion, see section 4.1.1) from any clinically significant toxicity experienced during treatment before the first dose of on study pembrolizumab therapy.	NA					
3.1.4	Eastern Cooperative Oncology Group (ECOG) performance status of 0 to 2	28 days		ECOG Date:			
3.1.5	Life expectancy of \geq 16 weeks.	NA					
3.1.6	Subjects must have measurable disease according to RECIST v1.1, and have baseline (screening/baseline) radiographic images, (e.g. CT, PET CT or MRI brain, chest, abdomen, pelvis, to be determined by the attending physician) within 4 weeks of confirmation of eligibility and within 6	4 weeks		Imaging Type: Imaging Date:			

	weeks before the initiation of on study pembrolizumab therapy.							
3.1.7	
Required values for initial laboratory tests:
 
 -WBC: $\geq 2000/\mu\text{L}$ ($\sim 2 \times 10^9/\text{L}$) -ANC: $\geq 1000/\mu\text{L}$ ($\sim 1 \times 10^9/\text{L}$) -Platelets: $\geq 50 \times 10^3/\mu\text{L}$ ($\sim 50 \times 10^9/\text{L}$) -Hemoglobin: $\geq 8 \text{ g/dL}$ -Calculated creatinine clearance (eGFR) greater than 30mL/min -AST/ALT: Less than 2.5 x ULN for subjects without liver metastasis, less than 5 times ULN for liver metastases -Bilirubin: less than 3.0 x ULN (except for subjects with Gilbert's Syndrome, who must have a total bilirubin of less than 3.0 mg/dL) -Non-clinically significant laboratory abnormalities such as lipase elevation would not be an exclusion. 	4 weeks		
Lab Date:
 
WBC:
 
ANC:
 
Platelets:
 
Hemoglobin
 
Creatinine clearance:
 
AST:
 
ALT:
 
Bilirubin:
				
3.1.8	
No known active or chronic infection with HIV, Hepatitis B, or Hepatitis C, or active infection requiring systemic antibiotics. Testing for the above is not required unless clinically suspected.
	NA						
3.1.9	
At least one measurable site of disease ($\geq 10 \text{ mm}$ as per RECIST v1.1 except for lymph nodes
	4 weeks						

	that must be 15 mm or greater on the short axis) outside of the planned palliative radiation therapy field.						
3.1.1.0	Require radiation therapy for palliation of symptoms or to prevent local progression of disease and associated complications and/or symptoms from metastases.	4 weeks					
3.1.1.1	Men and women, at least 18 years of age.	NA					
3.1.1.2	
Women of childbearing potential (WOCBP) must be using an adequate method of contraception to avoid pregnancy throughout the study [and for up to 26 weeks after the last dose of investigational product] in such a manner that the risk of pregnancy is minimized.
 
WOCBP include any female who has experienced menarche and who has not undergone successful surgical sterilization (hysterectomy, bilateral tubal ligation, or bilateral oophorectomy) or is not postmenopausal. Postmenopausal is defined as:
 
 • Amenorrhea \geq 12 consecutive months without another cause, or 	6 week before therapy		Preg. Test Date:			

	
 For women with irregular menstrual periods and on hormone replacement therapy (HRT), a documented serum follicle stimulating hormone (FSH) level > 35 mIU/mL 
Women who are using oral contraceptives, other hormonal contraceptives (vaginal products, skin patches, or implanted or injectable products), or mechanical products such as an intrauterine device or barrier methods (diaphragm, condoms, spermicides) to prevent pregnancy, or are practicing abstinence or where their partner is sterile (e.g., vasectomy) should be considered to be of childbearing potential. WOCBP must have a negative serum or urine pregnancy test (minimum sensitivity 25 IU/L or equivalent units of HCG) within 6 week prior to the start of investigational product.
						
3.1.1.3	Men of fathering potential must be using an adequate method of contraception to avoid conception throughout the study [and for up to 26 weeks after the last dose of investigational product] in such a manner that the risk of pregnancy is minimized.	NA					

	Conditions for Patient Ineligibility						
3. 2. 1	WOCBP who are unwilling or unable to use an acceptable method to avoid pregnancy for the entire study and for up to 26 weeks after the last dose of investigational product.	NA					
3. 2. 2	Women who are breastfeeding.	NA					
3. 2. 3	WOCBP with a positive pregnancy test within 6 weeks before enrollment.	6 week before therapy		Preg. Test Date:			
3. 2. 4	Autoimmune disease: Poorly controlled autoimmune disease is excluded. Well controlled autoimmune disease (e.g. well controlled RA) will be assessed by the study team and a decision made regarding eligibility based on the degree of immunosuppression and severity of symptoms.	NA					
3. 2. 5	Any subject who has a life-threatening condition that requires high-dose immunosuppressant(s). Steroid doses greater than 20 mg/day will exclude the patient from participation in the trial.	NA					
3. 2. 6	Presence of known hepatitis B or hepatitis C infection, regardless of control on antiviral	NA					

	therapy.						
3. 2. 7	Subjects who have another active, concurrent, malignant disease are not eligible, with the exception of subjects with adequately treated basal or squamous cell skin cancer, superficial bladder cancer, carcinoma in situ of the cervix, or other cancers that are in remission/not measurable. Patients will be excluded if they have any known additional malignancy that requires active treatment while on treatment for Merkel Cell Carcinoma.	NA					
3. 2. 8	Evidence of symptomatic interstitial lung disease or symptomatic active, noninfectious pneumonitis.	NA					
3. 2. 9	Participants with impaired cardiac function or clinically significant cardiac disease such as unstable angina/uncompensated heart failure, uncontrolled symptomatic arrhythmia.	NA					
3. 2. 1 0	Chronic or current active infectious disease requiring systemic antibiotics, antifungal, or antiviral treatment. This exclusion does not include prophylactic antibiotics or topical antibiotics.						
3. 2.	Known hypersensitivity to another monoclonal	NA					

1 1	antibody, which cannot be controlled with standard measures (e.g. antihistamines and corticosteroids).						
3. 2. 1	Any condition that would, in the investigator's judgment, interfere with full participation in the study.	NA					
3. 2. 1 3	Prisoners or subjects who are involuntarily incarcerated.	NA					
